7.1.1.3. Target volumes

7.1.1.3.1 Clinical target volume (CTV)

There are two clinical target volumes: CTV1 and CTV2.

CTV1 is the prostate plus a portion of or entire seminal vesicles. The extent of seminal vesicles to be included in CTV1 is at the judgement of the attending physician and based on clinical and pathologic features of a given malignancy.

CTV2 is the regional pelvic nodes. CTV2 includes the obturator, external iliac, proximal internal iliac and common iliac nodes, up to a level corresponding to the sacral promontory so that most of the common iliac nodes are included. Please refer to the pelvic nodal atlas at the RTOG Web site (Pelvic Lymph Node Volumes for Prostate Cancer Atlas;

██████████ The presacral nodes from the sacral promontory to S3 may be included, depending on whether the dose constraints to the rectum are achievable. The inferior extent of the external iliac lymph nodes is generally at the top of the femoral heads. The inferior extent of the obturator lymph nodes is generally at the top of the symphysis pubis. CTV2 will include a 7 mm margin in 3-dimensions to the iliac vessels, and a 10 mm margin anteriorly from the anterior sacral bone for presacral nodes. Adjacent normal organs (such as small bowel, large bowel, bladder, and rectum), pelvic musculature, and bones are carved out from CTV2.

7.1.1.3.2 Internal target volume (ITV)

ITV is an additional margin around CTV to ensure proper dose coverage of CTV, given changes in the dose distribution caused by target motion.

ITV1: CTV1 + 4-5 mm expansion for superior, inferior, anterior, and posterior directions, and 5-6 mm expansion in the lateral direction.

ITV2: CTV2 + 5 mm expansion in all directions

7.1.1.3.3 Optimization target volume (OTV): A volume constructed by a dosimetrist under the guidance of a physicist. The OTV is a volume used by the treatment-planning-dose-optimization algorithm to ensure that the ITVs and CTVs are treated with a planned radiation dose. It includes set-up and range uncertainties of 3 mm and 3 %, respectively. The OTV is to provide a robust coverage of CTV and ITV. The evaluation of a proton plan is based on a robust coverage of CTV and ITV. The OTV should not be considered when evaluating the treatment plan.

7.1.1.4 Normal Critical Structures

Normal critical structures to be defined on the treatment planning CT scan include the bladder, rectum, large bowel, small bowel, bilateral femora (to the level of ischial tuberosity), penile bulb, and skin. The structures will be contoured and considered as solid organs. The bladder should be contoured from its base to the dome, and the rectum from the anus (at the level of the ischial tuberosity) to the rectosigmoid flexure. Any small bowel within the primary beam aperture should be defined. Please refer to the RTOG web site

view the normal pelvis atlas for examples of target and normal tissue contours.

7.1.1.5 Treatment planning for critical structures

Plan quality and acceptability will be assessed in accordance to dose-volume histogram (DVH) parameters of target volumes and organs at risk (OAR) using the constraints shown in the following Table.

Target DVH Objectives		Priority
CTV	Max[Gy]	Report
	Max[%]	Report
	Min[Gy]	Report
	Min[%]	Report
	Mean[Gy]	Report
	D2%[%]	Report
	D5%[%]	Report
	D95%[%]	Report
	D98%[%]	100% (via normalization)
		Report

	V110%[cc] V98%[%] V99%[%]		Report Report Report
	V100%[%]	98% (via normalization)	1
	V107%[%] Volume[cc]		Report Report
	CV98%[%] CV98%[cc]		Report Report
ITV	Max[Gy] Max[%]	< 105%	Report 1
	Min[Gy] Min[%]	>90%	Report 3
	Mean[Gy] D2%[%]	<= 104 %	Report 3
	D5%[%]		Report
	D95%[%]	>= 95 %	3
	D98%[%]		Report
	V110%[cc]	0 cc	1
	V98%[%]	>= 98 %	1
	V99%[%]	>= 98 %	2
	V100%[%]	>= 95 % (or 95%)	2 (or 1, normalization)
	V107%[%]	<= 2 %	1
	Volume[cc]		Report
	CV98%[%]	<= 2 %	1
	CV98%[cc]		Report

Normal Tissue DVH Objectives			Priority
Bladder	D2cc[Gy]	< 72.91 Gy < 72.14 Gy	1 2
	V36Gy[cc] V57Gy[cc] V61Gy[cc] V66Gy[cc]		Report Report Report Report
	V36Gy[%]	33% 17%	1 2
	V57Gy[%]	15% 9%	1 2
	V61Gy[%]	11% 8%	1 2
	V66Gy[%]	8% 5%	1 2
	Volume[cc]		Report
	Right femoral head	Max[Gy]	< 34.96 Gy < 32.69 Gy
		Mean[Gy]	<= 23.95 Gy <= 18.28 Gy
		V32Gy[%]	<= 5% <= 2%
			1 2

	V14Gy[%]	<= 91% <= 66%	1 2
Left femoral head	Max[Gy]	< 34.96 Gy < 32.69 Gy	1 2
	Mean[Gy]	<= 23.95 Gy <= 18.28 Gy	1 2
	V32Gy[%]	<= 5% <= 2%	1 2
	V14Gy[%]	<= 91% <= 66%	1 2
Rectum	D2cc[Gy]	< 71.54 Gy < 71.19 Gy	1 2
	V44Gy[cc]		Report
	V53Gy[cc]		Report
	V57Gy[cc]		Report
	V61Gy[cc]		Report
	V66Gy[cc]		Report
	V44Gy[%]	24% 18%	1 2
	V53Gy[%]	17% 14%	1 2
	V57Gy[%]	15% 11%	1 2
	V61Gy[%]	12% 9%	1 2
	V66Gy[%]	9% 6%	1 2
Penile bulb	Mean[Gy]		Report
	D50%[Gy]	<= 47 Gy	2
	D70%[Gy]	<= 36 Gy	3
Large bowel	D2cc[Gy]		Report
	V44Gy[cc]		
	V53Gy[cc]		
	V57Gy[cc]		
	V61Gy[cc]		
	V44Gy[%]	24% 18%	1 2
	V53Gy[%]	17% 14%	1 2
	V57Gy[%]	15% 11%	1 2
	V61Gy[%]	12% 9%	1 2
	V66Gy[%]	9% 6%	1 2
Small bowel	Max[Gy]	< 52 Gy	3
	D2cc[Gy]		Report
	V30Gy[cc]	< 300 cc	3
	V45Gy[cc]	< 150 cc	2
	V50Gy[cc]	< 2 cc	3

Body - OTV	V50%[cc] V100%[cc] V105%[cc]	0 cc	Report Report 1
------------	------------------------------------	------	-----------------------

For purposes of compliance, up to a 5% absolute increase in the volume of critical structure receiving a specified dose (or higher) will be considered acceptable and called “minor deviation”. When there is a $\geq 5\%$ absolute increase in the volume of critical structure receiving a specified dose (or higher), it will be considered unacceptable and called a “major deviation”. [Example: rectum V66Gy $< 14\%$, but $> 9\%$: minor deviation; rectum V66Gy $\geq 14\%$ major deviation]

Of note, the penile bulb constraint is to be regarded as a guideline, and adherence to this should not, in any way, result in a reduction of the prescription dose or a compromised dose coverage of the target volume.

The deviations in dose constraints described above are considered planning deviations only and will not constitute protocol deviations. Treatment plans that include minor planning deviations may be delivered as part of this protocol. Treatment plans that include major planning deviations may be delivered on this protocol with the review and approval of the attending physician prior to treatment. All relevant DVH data regarding doses to critical structures will be maintained in the study database for analysis.

7.1.2 Target Dose

A prescribed dose of 67.5 Gy in 25 fractions (2.7 Gy per fraction per day, 5 days a week) is delivered to ITV1, while ITV2 is concurrently treated to a dose of 45 Gy in 25 fractions (1.8 Gy per fraction).

7.1.3 Treatment Administration

An optimal, pencil beam, proton therapy plan is prepared to achieve proper dose coverage of ITVs. Plan quality and acceptability is assessed, based on dose-volume histogram parameters of target volumes and organs at risk.

7.1.4 Treatment localization and verification

7.1.4.1 Patient set-up for daily proton beam therapy is identical to the CT simulation set-up, including bladder preparation and the application of endorectal balloon, if used. An endorectal balloon is inflated with 100 mL of normal saline (or, if necessary, diluted contrast consisting of 10 mL Gastroview mixed with 90 mL normal saline).

7.1.4.2 On-line target localization and image-guided proton beam therapy:

7.1.4.2.1 Use of implanted carbon fiducial markers

Daily kV orthogonal imaging of the implanted, intra-prostatic, carbon markers (from an on-board imager) should be used to

confirm the treatment set-up and to account for inter-fraction motion. A patient's position should be adjusted, using the fiducial markers as references.

7.1.4.1.2 Use of volumetric imaging with CT on a rail

The use of volumetric imaging with CT on a rail is strongly encouraged, if available, but not mandatory. Volumetric imaging is taken with a CT scan on a rail, after a treatment set-up is established using kV orthogonal imaging of the fiducial markers. This is to verify that ITV is properly covered volumetrically. Volumetric imaging is taken daily for the first 5 treatments and then twice weekly (every Monday and Thursday) thereafter.

7.2 Concurrent androgen deprivation therapy

As part of the standard of care, adjuvant androgen deprivation therapy is added to proton beam therapy for 2-3 years for high risk prostate cancer, and 4-6 months for intermediate risk prostate cancer. Androgen deprivation therapy usually starts 2 months prior to the beginning of proton beam therapy. It consists of bicalutamide 50 mg PO once daily for 2-16 weeks (given at the start of androgen deprivation therapy) and a LHRH agonist (goserelin or leuprolide). The first injection of a LHRH agonist is usually given within 7 days after the initiation of bicalutamide.

8.0 Radiotherapy Dose Modifications Based on Adverse Events

With judicious use of ancillary treatment (see Section 9.0) and/or treatment interruption, it is anticipated that a dose reduction should rarely be necessary. This study has no pre-specified dose reduction due to adverse events. However, if adverse events are severe enough that administration of full dose is considered contraindicated by the attending Radiation Oncologist, the study chair [REDACTED] should be notified.

Treatment interruption(s) are permitted only when radiation-related adverse events are not reduced to an acceptable level with the use of ancillary treatment (see Section 9.0), or when acute grade ≥ 3 AEs occur. The reason(s) for the interruption must be documented. The duration of treatment interruption should be minimized, but proton beam therapy should not resume until AEs are grade < 3 .

9.0 Ancillary Treatment/Supportive Care

Supportive measures such as antiemetic or antidiarrheal medications, steroid-containing topical preparations, topical bladder analgesic (e.g., phenazopyridine HCl) or anti-spasmodic (e.g., α -adrenergic blockers) agents may be administered in accordance with manufacturer recommendations as deemed necessary.

10.0 Adverse Event (AE) Reporting and Monitoring

10.1 Definitions

Adverse Event- An untoward or undesirable experience associated with the use of a medical product (i.e. drug, device, biologic) in a patient or research subject.

Serious Adverse Event - Adverse events are classified as serious or non-serious. Serious problems/events can be well defined and include;

- death
- life threatening adverse experience
- hospitalization secondary to radiation treatment, RT side effects or problem due to prostate carcinoma
- inpatient, new, or prolonged; disability/incapacity
- persistent or significant birth defect/anomaly

and/or per protocol may be problems/events that in the opinion of the investigator may have adversely affected the rights, safety, or welfare of the subjects or others, or substantially compromised the research data.

All adverse events that do not meet any of the criteria for serious, should be regarded as non-serious adverse events.

Unanticipated Problems Involving Risks to Subjects or Others (UPIRTSO) - Any unanticipated problem or adverse event that meets the following three criteria:

- **Serious**: Serious problems or events that result in significant harm, (which may be physical, psychological, financial, social, economic, or legal) or increased risk for the subject or others (including individuals who are not research subjects). These include: (1) death; (2) life threatening adverse experience; (3) hospitalization - inpatient, new, or prolonged; (4) disability/incapacity - persistent or significant; (5) birth defect/anomaly; (6) breach of confidentiality and (7) other problems, events, or new information (i.e. publications, DSMB reports, interim findings, product labeling change) that in the opinion of the local investigator may adversely affect the rights, safety, or welfare of the subjects or others, or substantially compromise the research data, **AND**
- **Unanticipated**: (i.e. unexpected) problems or events are those that are not already described as potential risks in the protocol, consent document, or not part of an underlying disease. A problem or event is "unanticipated" when it was unforeseeable at the time of its occurrence. A problem or event is "unanticipated" when it occurs at an increased frequency or at an increased severity than expected, **AND**
- **Related**: A problem or event is "related" if it is possibly related to the research procedures.

Preexisting Condition- A preexisting condition is one that is present at the start of the study. A preexisting condition should be recorded as an adverse event if the frequency, intensity, or the character of the condition worsens during the study period. At screening, any clinically significant abnormality should be recorded as a preexisting condition. At the end of the study, any new clinically significant findings/abnormalities that meet the definition of an adverse event must also be recorded and documented as an adverse event.

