7.0 Protocol Treatment

Protocol treatment consists of proton beam therapy, in combination with 28 months of androgen deprivation therapy (or 4-6 months of androgen deprivation therapy for intermediate risk prostate cancer).

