10.5.1 Medical Monitoring

It is the responsibility of the Principal Investigator to oversee the safety of the study at his site. This safety monitoring will include careful

assessment and appropriate reporting of adverse events as noted above, as well as the construction and implementation of a site data and safety-monitoring plan. Medical monitoring will include a regular assessment of the number and type of serious adverse events. Any serious adverse events will be followed up by the sentinel event reporting procedure.

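### Section 10.1 gives two inconsistent hospitalization criteria for a serious event, so an admission not caused by radiation or prostate cancer, including one caused by protocol hormone therapy, can be left out of the SAE counts

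*Combined protocol and SAP*

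**What the plan says.** Section 10.1 lists what makes an adverse event serious. After death and life-threatening events comes "hospitalization secondary to radiation treatment, RT side effects or problem due to prostate carcinoma". The next bullet, as printed, is "inpatient, new, or prolonged; disability/incapacity". The list ends with a clause resting on judgement: "and/or per protocol may be problems/events that in the opinion of the investigator may have adversely affected the rights, safety, or welfare". The default follows: "All adverse events that do not meet any of the criteria for serious, should be regarded as non-serious adverse events".

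The UPIRTSO paragraph in the same section has its own list of serious problems. Its items include "3) hospitalization - inpatient, new, or prolonged; (4) disability/incapacity - persistent or significant". No cause is attached to hospitalization there. A UPIRTSO must be serious, unanticipated and related, and these are three separate tests. Section 10.2.1 also makes relatedness its own step, after the event has been identified and graded, and Section 10.2.2 supplies the five attribution categories.

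On treatment, Section 7.0 states: "Protocol treatment consists of proton beam therapy, in combination with 28 months of androgen deprivation therapy" (4-6 months for intermediate-risk disease). Section 7.2 describes the same hormone therapy as standard of care.

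Two provisions act on SAE status. Section 10.5.1 says: "Medical monitoring will include a regular assessment of the number and type of serious adverse events", and it sends every SAE to sentinel-event follow-up. Section 10.3.1.1 sets the 5-working-day report to the IRB for an SAE that the principal investigator has judged to be a UPIRTSO.

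**The concern.** The SAE bullet builds a causal judgement into the definition of seriousness. Elsewhere the protocol keeps the two apart: in the UPIRTSO criteria, in Section 10.2.1 and in Section 10.2.2. Two people applying Section 10.1 to the same admission can therefore classify it differently, depending on which list they use.

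The bullet names the radiation and the cancer but not androgen deprivation therapy, although Section 7.0 makes that therapy part of protocol treatment. At stake is the completeness of the SAE counts in a single-arm trial whose primary goal is toxicity. An admission first judged to have another cause is the kind of event that a monitor would want to see, in case a pattern emerges.

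**Working it through.** The plan gives no figure on this point and no arithmetic decides it. The check sets the two lists side by side and then follows SAE status to where it is used.

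**Step 1. Classify typical admissions under each list.** Assume that no other criterion (death, life-threatening, disability) is met.

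| Reason for admission | SAE hospitalization bullet | UPIRTSO serious list |
|---|---|---|
| Side effect of proton therapy | Met | Met |
| Problem due to prostate cancer | Met | Met |
| Complication of androgen deprivation therapy | Not met: neither named cause | Met |
| Possibly, but not clearly, due to radiation | Unclear: the bullet requires the admission to be secondary to it | Met |
| Judged to have some other cause | Not met | Met |

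The lists agree on the first two rows and part on the other three.

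**Step 2. Apply the default.** An admission that fails the bullet is non-serious unless another criterion or the investigator-opinion clause brings it in. That clause is discretionary and does not mention hospitalization, whereas the UPIRTSO item is categorical.

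**Step 3. Follow SAE status downstream.**
- Section 10.5.1: an admission not classed as an SAE is absent from the assessment of SAE number and type, and from sentinel-event follow-up.
- Section 10.3.1.1: the wording starts from an SAE and then asks whether it is a UPIRTSO. Read literally, a possibly related, unanticipated admission could meet all three UPIRTSO criteria and still not enter this pathway, because it was never an SAE.

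**Step 4. Gauge how long the unnamed component is given.** Assume that the 28 months run from the start of hormone therapy, that it starts the usual 2 months before radiation (Section 7.2), and that radiation lasts 5 weeks (Section 1.4). Then 5 / (52/12) ≈ 1.2 months, and 28 − 2 − 1.2 ≈ 24.8 months of hormone therapy remain after radiation ends. On those assumptions it spans the whole 24-month active monitoring period in high-risk men. This describes exposure. It is not a count of admissions, for which the documents give no rate.

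**Step 5. Check the statistical design.** The primary endpoint (Sections 16.1.1 and 16.3.1) and the stopping rule (Section 16.4.2) use toxicity grade, attribution and timing. Neither uses seriousness. The 51-patient decision rule and its tabulated probabilities are unchanged whichever list applies.

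**The case against.** The case on the other side is substantial.

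- **The list is not closed.** It is introduced as what serious events include, and it has the investigator-opinion clause. A reader might infer that no other hospitalization can ever be an SAE; the text does not support that. What stands is that inclusion then depends on discretion or on another criterion.
- **The bullets after hospitalization look misaligned.** A reader might count this as a second defect. Rejoined, the fragments follow the wording and order of the UPIRTSO list, so a formatting fault, in the source or in text extraction, is the likelier explanation. Rejoining them leaves the causal qualifier in place, so the point does not rest on them.
- **Other review does not depend on SAE status.** Section 10.1 defines a UPIRTSO as any unanticipated problem or adverse event meeting its criteria, so an investigator can reach it directly. Section 10.3 has the investigator review all adverse event reports, and Section 10.3.1.2 sends non-UPIRTSO events to the IRB in summary. Section 16.4.1 provides reviews at least twice a year by the investigators and statistician and at least yearly by the DSMB. The text after the stopping rules in Section 16.4.2 re-checks attribution of grade 4 and 5 events called unrelated or unlikely. Section 18.1 has a form for other adverse events. It would therefore be wrong to infer that these admissions go unseen. What stands is that the attribution re-check stops at grade 4 and 5, and that none of these provisions restores an admission to the SAE counts.
- **The narrowing may be deliberate.** Section 7.2 calls hormone therapy standard of care, and the primary endpoint concerns proton therapy alone. The documents give no such rationale, however, and the conflict with the UPIRTSO list and with Section 7.0 would remain.
- **The effect on IRB reporting is limited.** Section 10.3 restricts IRB reports to directly related SAEs/UPIRTSOs, so correcting the definition would not by itself send unrelated admissions to the IRB.

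**Conclusion.** The inconsistency is real and lies within one section. As written, a hospitalization from a cause other than radiation or prostate cancer, including one caused by androgen deprivation therapy, is an SAE only through another criterion or the investigator's discretion. It can then be missing from the counts and follow-up in Section 10.5.1. On a literal reading of Section 10.3.1.1 it may also not enter the 5-day pathway; that part depends on taking SAE as a precondition there, which the UPIRTSO definition itself does not require.

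The size cannot be estimated from the documents, because no admission rate is given. The effect is confined to SAE classification and the processes that use it. A reader might infer that the trial's toxicity result or its early stopping is compromised. The documents do not support that, since both rest on grade, attribution and timing. This is a wording inconsistency in safety reporting that is worth correcting, with other safeguards covering part of the gap.

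**What to change.** Reconcile the two lists in Section 10.1. In the SAE definition, replace the hospitalization bullet with the unqualified UPIRTSO item (inpatient, new or prolonged), and realign the disability and birth-defect items with that list at the same time. Leave cause to the existing attribution step in Section 10.2.2. Recording attribution separately for proton therapy and for androgen deprivation therapy would be a useful option, but the correction does not require it.

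The change is to wording only. Sample size, visits, endpoint definitions and stopping rule stay as they are. The cost is that somewhat more unrelated hospitalizations will be logged as SAEs and will pass through the follow-up in Section 10.5.1. Those that are not UPIRTSOs can use the summary route at continuing review that Section 10.3.1.2 already provides.

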10.2 Recording Adverse Events

CTCAE term (AE description) and grade: The descriptions and grading scales found in the revised NCI Common Terminology Criteria for Adverse Events (CTCAE) version 4.0 will be utilized for AE reporting. All appropriate treatment areas should have access to a copy of the CTCAE version 4.0. A copy of the CTCAE version 4.0 can be downloaded from the CTEP web site:

[REDACTED]

10.2.1 Adverse event monitoring and reporting is a routine part of every clinical trial. First, identify and grade the severity of the event using the CTCAE version 4.0. Next, determine whether the event is expected or unexpected and if the adverse event is related to the medical treatment or procedure. With this information, determine whether the event must be reported as an expedited report (see Section 10.3).

10.2.2 Assessment of Attribution

When assessing whether an adverse event is related to a medical treatment or procedure, the following attribution categories are utilized:

Definite - The adverse event is clearly related to the agent(s).

Probable - The adverse event is likely related to the agent(s).

Possible - The adverse event may be related to the agent(s).

Unlikely - The adverse event is doubtfully related to the agent(s).

Unrelated - The adverse event is clearly NOT related to the agent(s).

